The power calculation, which was based on Pearson Chi Square test, assumes the following:

- One-sided Type I error rate of 0.05
- Anticipated positive NP samples rate of 30% in the clinical arm
- A 40% lower risk of a positive NP sample comparing the hydroxychloroquine group vs the controls
- Loss to follow-up rate of 15%

Primary analysis of efficacy:

The proportion of individuals who tested positive at least once during the study period will be compared between the clinical and the control arms. In addition, the potential effect of hydroxychloroquine on COVID-19 free survival time will also be explored by utilizing appropriate statistical methods. An intent-to-treat approach will be used throughout the analysis with the control group as the referent. A p-value < 0.05 will be considered statistically significant and a risk reduction of 5% will be considered as of smallest clinical importance.

Study Rationale

It is clear that close interaction of health care workers with patients put them at higher risk of getting exposed to infectious diseases. Failing to provide a safe environment for health care workers could cripple the medical system especially during an Epidemic outbreak like COVID-19. It is imperative to make sure that doctors and nurses do not get sick in high numbers; not only because that will contribute to spreading the virus among vulnerable patients but also due to their subsequent role in reducing the number of responding personnel. As a result, it is of utmost importance to provide effective prophylaxis to healthcare workers who are exposed to COVID-19.

Schema for Study of Prophylactic Therapies for COVID-19 Exposure

The trial design is initially for a 7 week treatment period which can be divided into 7 bins of time to allow a flexible design. Given the fluid nature of information flow in this pandemic that for example, new information comes forward clearly showing that 6 days is a sufficient period of time for proven prophylaxis, this trial design can be altered. Conversely if each subsequent qualifying exposure calls for another 6-day bin of time, the protocol can flex to the maximum 7 week period as stated for resource planning.

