5. INTRODUCTION

New major epidemic foci of coronavirus disease 2019 (COVID-19), have been identified and are rapidly expanding in Europe, North America, Asia, and the Middle East, with the first confirmed cases being identified in African and Latin American countries.¹ By March 16, 2020, the number of cases of COVID-19 outside China had increased drastically and the number of affected countries, states, or territories reporting infections to WHO was 143.1 On the basis of “alarming levels of spread and severity, and by the alarming levels of inaction”, on March 11, 2020, the Director-General of WHO characterized the COVID-19 situation as a pandemic.

The WHO Strategic and Technical Advisory Group for Infectious Hazards (STAG-IH) regularly reviews and updates its risk assessment of COVID-19 to make recommendations to the WHO health emergencies programme.² STAG-IH's most recent formal meeting on March 12, 2020, included an update of the global COVID-19 situation and an overview of the research priorities established by the WHO Research and Development Blueprint Scientific Advisory Group that met on March 2, 2020, in Geneva, Switzerland, to prioritize the recommendations of an earlier meeting on COVID-19 research held in early February, 2020.

To respond to COVID-19, many countries are using a combination of containment and mitigation activities with the intention of delaying major surges of patients and levelling the demand for hospital beds, while protecting the most vulnerable from infection, including elderly people and those with comorbidities. Activities to accomplish these goals vary and are based on national risk assessments that many times include estimated numbers of patients requiring hospitalization and availability of hospital beds and ventilation support. Most national response strategies include varying levels of contact tracing and self-isolation or quarantine; promotion of public health measures, including handwashing, respiratory etiquette, and social distancing; preparation of health systems for a surge of severely ill patients who require isolation, oxygen, and mechanical ventilation; strengthening health facility infection prevention and control, with special attention to nursing home facilities; and postponement or cancellation of large-scale public gatherings.

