7.3. Treatment Assignment

Qualified individuals may choose which group they want to be in. Subjects in the treatment group will receive hydroxychloroquine for 7 weeks. Those who decide to opt out of receiving treatments will compose the control group.

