18 APPENDICES

18.1 Appendix I: Registry for Screened and Not Randomized

For healthcare workers who have been screened and who would have qualified as eligible subjects but decline participation because of personal choice or logistical reasons, a registry will be offered with the same baseline data collection, schedule of NP sampling, and capture of outcomes. This will serve as a form of community surveillance for the medical center and will have a sample size that will not be pre-specified and limited only by the availability of NP COVID-19 sampling. For those who develop a positive NP test, the current guidance from the medical center administration and in concert with guidance from the U.S Federal Government, State and Local Authorities, Centers for Disease Control, and State and Local Health Departments, will all be applied in terms of next steps in monitoring and control of COVID-19 viral spread.

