2.1. Sample size calculation

A total sample of 360 individuals (180 in each arm) would provide at least 80% power to detect a relative risk reduction of 40% in the rate of positive NP samples when the anticipated rate of positive conversion among those taking hydroxychloroquine is approximately 30%.

The power calculation, which was based on Pearson Chi Square test, assumes the following:

- One-sided Type I error rate of 0.05
- Anticipated positive NP samples rate of 30% in the clinical arm
- A 40% lower risk of a positive NP sample comparing the hydroxychloroquine group vs the controls
- Loss to follow-up rate of 15%

3. Aims and objectives

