6.1. Primary Analysis of Efficacy

All subjects who received at least one dose of study medication, will be used as the primary population for assessment of efficacy. The proportion of people whose NP sample becomes positive at least once during the trial will be compared between the study groups using Chi square or Fisher exact test. Survival analysis will be utilized to estimate the potential effects of hydroxychloroquine on COVID-19 free survival times. We will apply generalized linear mixed models to compare the positive conversion rate of COVID-19 between the study arms while controlling for other confounding factors. AIC and BIC criteria will be used to choose an appropriate covariance structure between the measurements collected at consecutive visits. An interaction effect between time and study group will be added to the model to evaluate whether the relative risk of a positive conversion changes from visit to visit.

7. Missing data

If the proportions of missing data are above 5%, multiple imputation methods will be used to construct complete data sets under different missing patterns. Otherwise, linear mixed models will be used that allow for presence of missing values in the data.

8. References

- ¹ Bedford J, Enria D, Giesecke J, Heymann DL, Ihekweazu C, Kobinger G, Lane HC, Memish Z, Oh MD, Sall AA, Schuchat A, Ungchusak K, Wieler LH; WHO Strategic and Technical Advisory Group for Infectious Hazards. COVID-19: towards controlling of a pandemic. *Lancet*. 2020 Mar 17. pii: S0140-6736(20)30673-5. doi:10.1016/S0140-6736(20)30673-5. [Epub ahead of print] PubMed PMID: 32197103
- ² Zhou D, Dai SM, Tong Q. COVID-19: a recommendation to examine the effect of hydroxychloroquine in preventing infection and progression. *J Antimicrob Chemother*. 2020 Mar 20. pii: dkaa114. doi: 10.1093/jac/dkaa114. [Epub ahead of print] PubMed PMID: 32196083.
- ³ Sahraei Z, Shabani M, Shokouhi S, Saffaei A. Aminoquinolines Against Coronavirus Disease 2019 (COVID-19): Chloroquine or Hydroxychloroquine. *Int J Antimicrob Agents*. 2020 Mar 16:105945. doi: 10.1016/j.ijantimicag.2020.105945. [Epub ahead of print] PubMed PMID: 32194152.
- ⁴ Devaux CA, Rolain JM, Colson P, Raoult D. New insights on the antiviral effects of chloroquine against coronavirus: what to expect for COVID-19? *Int J Antimicrob Agents*. 2020 Mar 11:105938. doi: 10.1016/j.ijantimicag.2020.105938. [Epub ahead of print] PubMed PMID: 32171740.

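### Calendar time enters no analysis although workers choose their group during a changing epidemic, so a shift in that choice over the enrolment weeks would bias the comparison in either direction

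*SAP*

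**What the plan says.** Protocol 7.3 lets participants pick: "Qualified individuals may choose which group they want to be in". The protocol synopsis plans 180 per group and a studied period of 4 months, from first enrolment in March 2020 to last completion in July 2020. Protocol 7.1 and SAP section 2 set seven weekly visits counted from each person's own enrolment.

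SAP 6.1 gives three analyses:
- a chi-square or Fisher test of the proportion ever positive, with no adjustment;
- a survival analysis, described only as "Survival analysis will be utilized to estimate the potential effects of hydroxychloroquine on COVID-19 free survival times", with no method, time origin, time scale or covariates;
- a generalised linear mixed model over visits, with a time-by-group interaction and adjustment for confounders that are not named.

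Appendix I of the protocol says the registry "will have a sample size that will not be pre-specified and limited only by the availability of NP COVID-19 sampling". On the epidemic, Protocol section 5 is qualitative: by mid-March 2020 "the number of cases of COVID-19 outside China had increased drastically". No local growth rate is given. No section balances or matches enrolment dates, stratifies by week, or names calendar time as a covariate or time axis.

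**The concern.** Infection pressure depends on the date; visit number depends on when a person joined. Two workers at the same visit can face very different risk. If drug takers tend to join in different weeks from registry members, their 7-week windows cover different parts of the epidemic and their conversion proportions differ even if the drug does nothing. This would happen even if the two groups were alike in every personal characteristic.

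The chi-square has no means of removing this, and the mixed model indexes visits, not dates. The planned interaction would not reveal it in the simplest case: with a fixed lag and exponential growth or decline, the false hazard ratio is the same at every visit. At stake is a false claim of benefit, or a real benefit hidden.

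**Working it through.** **Design figure.** SAP 2.1 uses "One-sided Type I error rate of 0.05", "Anticipated positive NP samples rate of 30% in the clinical arm", 15% loss, and says 360 people "would provide at least 80% power to detect a relative risk reduction of 40" per cent. With 30% as the control rate and 18% on drug (mean 0.24), the pooled chi-square formula gives

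n = [1.645·√(2·0.24·0.76) + 0.842·√(0.30·0.70 + 0.18·0.82)]² / 0.12² = 156 per arm.

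Then 156 × 1.15 gives 180 per arm, or 360; 156/0.85 gives 184, or 368. Power at 153 evaluable per arm is 79.4%. Reading 30% as the drug-arm rate, as written, gives 176 in total, so 360 reproduces only with 30% as the control rate (a separate matter). The design relative risk is 0.60. As a hazard ratio it is ln(0.82)/ln(0.70) = 0.556.

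**Enrolment window.** Four months is about 17 weeks; less 7 weeks of follow-up leaves about 10.

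**Fixed lag, no drug effect.** If incidence doubles or halves every T weeks and one group joins L weeks away from the other, HR = 2^(−L/T). With 30% in the higher-risk group, the other group's risk is 1 − 0.70^HR.
- T = 4, L = 2: HR 0.707, risk 22.3%, RR 0.74 (or 1.35 with the groups reversed).
- T = 3 or 8, L = 2: RR 0.67 or 0.86.
- T = 4, L = 4: HR 0.50, risk 16.3%, RR 0.54.

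The lag that gives HR 0.556 is 1.7, 2.5, 3.4 and 6.8 weeks for T = 2, 3, 4 and 8. With 153 per arm and one-sided 0.05, a drug-favouring 2-week lag at T = 4 makes the chi-square reject 46% of the time. (The synopsis rule, "A p-value < 0.05 will be considered statistically significant", does not state sides.)

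**Drift in choice, no drug effect.** Let the share choosing drug fall linearly from a to b over 10 weeks (a + b = 1). The mean lag between groups is 10(a − b)/3 weeks. A person joining in week c has cumulative hazard H(c) = h₀·2^(c/T)·(2^(7/T) − 1)·T/ln 2 and risk 1 − exp(−H(c)). I averaged this over c with weights s(c) and 1 − s(c), where s(c) is the share choosing drug in week c, and set h₀ for 30% overall. The false RR on a rising curve is:

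| Share on drug | Mean lag (weeks) | T = 2 | T = 3 | T = 4 | T = 8 |
|---|---|---|---|---|---|
| 50% throughout | 0 | 1.00 | 1.00 | 1.00 | 1.00 |
| 60% → 40% | 0.67 | 0.85 | 0.89 | 0.91 | 0.95 |
| 70% → 30% | 1.33 | 0.72 | 0.79 | 0.83 | 0.91 |
| 80% → 20% | 2.0 | 0.61 | 0.70 | 0.76 | 0.87 |
| 95% → 5% | 3.0 | 0.46 | 0.58 | 0.66 | 0.81 |

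On a falling curve, or with drift the other way, the values invert (0.76 becomes 1.32).

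**Simulation** (306 evaluable, 100 replicates per scenario, T = 2 and 3 only; slower epidemics rest on the formulas). The simulated RRs agree with the table to within 0.04. A Cox model on study time gave HR 0.54 and 80% rejection at T = 2 with 80% → 20% drift, and up to 98% rejection at 95% → 5%. With no drift it rejected 3% of the time. A Cox model on calendar time with delayed entry, or stratified by enrolment week, gave HR 0.93–1.06 and 0–9% rejection throughout, which is noise around 5%.

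**The case against.** The strongest case against is that no document shows the share changing. Eligible workers choose within one centre and one recruitment period, so enrolment is broadly concurrent, and with balanced choice there is nothing to correct. That stands, and it makes the size conditional. It does not remove the gap, because nothing enforces balance and the protocol synopsis itself expects information to move quickly, which can move preferences.

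The mixed model's open confounder clause and the exposure questionnaire at every visit (Protocol 9.8.12) could offset part of the bias. But the clause names no variable, no analysis uses the questionnaire, and it records exposure at work, not background incidence.

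A reader might infer more than the documents support:
- *That the survival analysis runs on study time.* This is plausible from the enrolment-based visits, but the SAP does not state it. The defect is silence, not a demonstrated wrong choice.
- *That the epidemic curve by itself yields the design effect.* It yields nothing without a difference in enrolment timing. With two 4-week enrolment windows and a 4-week halving time, the 4-week lag that passes 0.60 means that one group finishes before the other starts.
- *That enrolment lasts 4 months.* That span includes follow-up.
- *That drug or swab supply separates the groups.* The synopsis ties drug supply to dispensing, and both groups need the same swabs.
- *That interval censoring adds to the bias.* With ±3-day windows, scheduled swabs can be 13 days apart (Day 4 to Day 17). Both groups share the schedule, so no differential bias is shown.

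**Conclusion.** The gap is real. Groups are self-chosen, enrolment dates are not balanced, and calendar time is in no analysis, including the unadjusted primary test.

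The size rests on an assumed growth rate and an assumed drift. At a 4-week doubling or halving time, mild to strong drift (60% → 40% to 80% → 20%) gives a false RR of about 0.91 to 0.76 or the inverse, and a 2-week lag gives about 0.74. The design RR of 0.60 is reached only with faster epidemics and strong drift (about 0.60 at 2-week doubling with 80% → 20%) or nearly separate enrolment. The documents do not support saying that a bias as large as the design effect is expected; they support saying that it is possible and that the plan would not remove it.

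**What to change.** In SAP 6.1:
- specify the survival analysis as a Cox model on calendar time with delayed entry at Day 1, or stratified by week of enrolment;
- add calendar week to the mixed model alongside visit, for example as a 3-degree-of-freedom spline;
- name one calendar-adjusted estimate as the basis of the main efficacy conclusion, with the unadjusted chi-square as supportive;
- tabulate enrolment dates by group.

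Restriction to the period when both groups were enrolling should be a sensitivity analysis only. With two 4-week windows 2 weeks apart it drops half of each group, leaving about 76 per arm and cutting power from 79% to about 54%.

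The cost is SAP wording and 2–3 degrees of freedom, using visit dates the study already holds. For power, take 153 × (0.30 + 0.18) = 73.4 events, HR 0.556 and v = 0.25 − (a − b)²/12 in Φ(√(73.4·v)·|ln 0.556| − 1.645). This gives 80.7% with no drift, 78.8% for 70% → 30%, 76.2% for 80% → 20% and 69.2% for 95% → 5%. The change removes bias from enrolment timing only; other differences between people who choose drug and people who decline it remain.

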5.2. Per Protocol (PP)

All randomised study subjects completing the whole study period (complete cases)

6. Analyses

All statistical analyses and data summaries will be performed using SAS® (Version 9.1 or higher) or other validated software. The SAP will serve as the final arbiter of all statistical analyses. Data will be summarized overall using descriptive statistics. Continuous data will be summarized with number of subjects (n), mean, median, minimum, maximum, relevant quartiles, standard deviation, coefficient of variation, and geometric mean (where applicable). Categorical data will be summarized using frequency counts and percentages. Chi Square or Fisher exact test will be used for comparing binary outcomes between treatment and control groups. Continuous variables will be compared between the study groups by means of two sample T test or Wilcoxon-rank-sum test.

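### The primary test ignores work unit and calendar time although workers choose their own group; its 5% error rate fails if infection and group choice both vary by these factors

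*SAP*

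**What the plan says.** Assignment is by preference. Protocol section 7.3 states: "Qualified individuals may choose which group they want to be in". Those who decline the drug become the controls. Protocol Appendix I describes a registry for eligible workers who decline, with a size "limited only by the availability of NP COVID-19 sampling".

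For the analysis, the opening of SAP section 6 states: "Chi Square or Fisher exact test will be used for comparing binary outcomes between treatment and control groups". Section 6.1 applies this to the proportion ever positive and adds two further analyses:

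- a survival analysis with no stated covariates;
- a generalized linear mixed model that adjusts for confounders it does not name. On correlation it says only: "AIC and BIC criteria will be used to choose an appropriate covariance structure between the measurements collected at consecutive visits". Its interaction term uses time as study visit, not epidemic week.

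The sample size in SAP section 2.1 rests on a Pearson chi-square test with "One-sided Type I error rate of 0.05" and lists no allowance for clustering. The Protocol Synopsis adds "A p-value < 0.05 will be considered statistically significant" without stating sidedness.

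Some unit information is already planned. The secondary objective compares emergency department (ED) with intensive care unit (ICU) workers, and the Appendix III questionnaire asks at each visit about shifts in the ICU, ED or another COVID unit.

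**The concern.** Chi-square and Fisher tests treat every worker as an independent observation. This is a contagious infection at a single centre over about four months, among staff who share patients and rooms. Outcomes within a unit, or within an epidemic period, may therefore be correlated.

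That alone does not harm the treatment comparison. Harm arises when group choice also differs between units or periods. An outbreak in a unit where most staff took the drug, or most declined it, then shows up as a treatment difference. Randomisation within units would prevent this, but here there is none, and nothing else aligns the groups by unit or week. At stake is whether a significant result, in either direction, can be attributed to the drug.

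**Working it through.** **The plan's own figure.** Per-arm size is n = [z(α)√(2p̄q̄) + z(β)√(p₁q₁ + p₀q₀)]² / (p₀ − p₁)², one-sided α = 0.05, 80% power.

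- Literal inputs ("Anticipated positive NP samples rate of 30% in the clinical arm", and 40% lower than controls, so 50% in controls): [1.645×0.693 + 0.842×0.678]² / 0.20² gives 74 per arm. 74/0.85 gives 88, a total of 176.
- If 30% is the control rate instead (18% on drug): [1.645×0.604 + 0.842×0.598]² / 0.12² gives 156 per arm. 156×1.15 = 179.4, so 180 per arm and 360 in total.

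The plan's 360 is therefore recovered only on the second reading. That mismatch is a separate matter. What counts here is that neither reading contains a design effect.

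**Inputs for the clustering check.** From the documents: 360 enrolled less 15% loss, so 306 evaluable, and a 30% event rate. Assumed, because the documents are silent: 6 or 12 equal units (m = 51 or 25.5 workers each), average uptake 50%, outcome ICC 0.02-0.10, between-unit SD of the share choosing the drug 0.15-0.35. There is no drug effect.

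**Formula.** The variance of the unstratified comparison is multiplied by about DE = 1 + (m − 1) × ICC(outcome) × ICC(choice), where ICC(choice) = SD²/(0.5×0.5). SDs of 0.15, 0.25 and 0.35 give 0.09, 0.25 and 0.49. The two-sided type I error is then about 2[1 − Φ(1.96/√DE)].

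| Units | ICC(outcome) | SD of choice | DE | Error by formula |
|---|---|---|---|---|
| 6 or 12 | any | 0 | 1 | 0.050 |
| 12 | 0.02 | 0.15 | 1 + 24.5×0.02×0.09 = 1.04 | 0.055 |
| 6 | 0.05 | 0.25 | 1 + 50×0.05×0.25 = 1.63 | 0.124 |
| 12 | 0.10 | 0.35 | 1 + 24.5×0.10×0.49 = 2.20 | 0.186 |
| 6 | 0.10 | 0.35 | 1 + 50×0.10×0.49 = 3.45 | 0.291 |

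**Simulation.** Beta-binomial simulation agrees: about 5%-28% over this grid, and about 11% for 6 units, ICC 0.05 and SD 0.25. With no clustering of choice, 8,000 runs per setting (6, 12 or 30 units) gave 0.044-0.056 whatever the outcome ICC. Read one-sided, the worst setting (6 units, outcome ICC 0.10, choice ICC 0.5) gave 0.173 instead of 0.278. A Cochran-Mantel-Haenszel test stratified by the simulated units stayed at 4%-6%.

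**Cost of stratifying by unit.** The information kept, relative to a balanced comparison, is about (1 − ICC(choice)) × (m − 1)/m. With no clustering of choice this is 24.5/25.5 = 0.96 to 50/51 = 0.98. At SD 0.15 it is 0.91×0.96 = 0.87 to 0.91×0.98 = 0.89. At SD 0.25 it is 0.72-0.74, and at SD 0.35 about 0.50. Simulation gave 87%-90%, 72%-74% and about 50%.

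**The case against.** The strongest reply is that the effect is conditional and undocumented. Both infection and choice must vary by unit or period, and the documents report neither. The Protocol Introduction describes clustering in families and says hospital transmission was not a major amplifier in China, which could argue for a small outcome ICC. At the mild end of the assumed ranges the inflation is trivial. This stands, and it limits how strongly the point can be put.

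A second reply is that the mixed model already adjusts for confounders. It could include unit and week, but the SAP commits to neither, and adjustment there does not repair the chi-square comparison, which the Synopsis puts first and on which the sample size rests.

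A third is that clustering matters more for the ED versus ICU objective, where the comparison is itself between units. That is true: with 51 workers per unit and outcome ICC 0.05, DE = 1 + 50×0.05×1 = 3.5. It does not remove the problem from the primary comparison.

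Three stronger readings are tempting, and the documents do not support them:

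- A reader might infer that the p-values and intervals are simply wrong. They are not if choice is unrelated to unit and period.
- A reader might infer that drug supply controls entry to the treated group, so that the groups enrol at different epidemic stages. The Synopsis ties supply to how far ahead drug is dispensed, not to enrolment.
- A reader might infer the same for controls from the swab limit in Appendix I. Both groups are swabbed weekly, so a shortage is not shown to affect only one. With no accrual pattern by group documented, no size can be put on calendar bias.

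**Conclusion.** The point holds in conditional form. For self-selected groups the plan names no work-unit or calendar factor in any efficacy analysis, and its headline test is unstratified. If infection and choice both vary by unit or calendar time, these are confounders: the estimate can be biased as well as its standard error too small, so a cluster-robust variance alone would not cure it.

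The type I error range of about 5%-28% rests wholly on the assumed unit numbers, ICCs and spread of choice. The upper end needs few units and strong clustering of both infection and choice. It shows what the plan leaves open and does not estimate what will happen in this trial. The change should be made because it is cheap and because the plan as written could read a unit outbreak as a drug effect.

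**What to change.** - Make the primary test a Cochran-Mantel-Haenszel test stratified by work unit in a few broad categories, for example ED, ICU and other COVID unit.
- Include unit and calendar time of swab as named covariates in the mixed and survival models.
- Record primary work unit as one baseline field. The weekly shift question and the ED versus ICU objective already go most of the way.
- Report uptake by unit and calendar period, so that readers can see whether choice clustered.

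Avoid fine strata of unit by two-week enrolment block. With an assumed five blocks and outcome ICC 0.05, simulation puts the information kept at 82% down to 41% over choice SD 0.15-0.35, because many strata hold only one group.

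The cost is SAP wording and one field. Stratifying by unit keeps about 96%-98% of the information if choice does not cluster. If it does, the loss is real, as shown in the working, and falls where the unstratified result is least trustworthy. Two limits remain. Workers who rotate may be misclassified by a single baseline unit. Broad categories also remove only differences between categories; the 4%-6% error rate was obtained with strata equal to the units themselves, so variation among units within a category is left to the model covariates.
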